Objectives: The primary efficacy objective is to compare the effect of the individualised treatment plan, relative to a minimal physiotherapeutic rehabilitation program, on changes in Shoulder Pain and Disability Index (SPADI) from baseline to 12 weeks after initiating the treatment, in women with late-term shoulder impairments after primary breast cancer surgery.

Methods: The study was designed as a randomised trial with a two-group comparison testing superiority hypothesis related to the primary and key secondary objectives. In total, 130 participants would randomised (allocation 1:1) to either an expert assessment of shoulder impairments followed by an individualised treatment plan or to follow a minimal physiotherapeutic rehabilitation program delivered in a pamphlet. The primary analysis will be based on the Intention to Treat (ITT) population; the ITT principle asserts the effect of a treatment policy (that is, the planned treatment regimen), rather than the actual treatment given (i.e., it is independent of treatment adherence). The analyses of the key secondary outcomes will be performed in a prioritized order. The analyses of the confirmatory secondary outcomes will be performed in sequence until one of the analyses fails to show the statistically significant difference, or until all analyses have been completed at a two-sided statistical significance level of 0.05. The continuous outcomes will be analysed based on Repeated-Measures Mixed Effects Models (time: 0, 4, 8, and 12 weeks from baseline).

Registration: ClinicalTrials.gov, identifier: NCT05277909. Registered on 11 March 2022.

INTRODUCTION

Breast cancer is the most common cancer in women worldwide. Standard surgical treatment in Denmark is breast-conserving surgery (BCS) or mastectomy in combination with sentinel lymph node dissection (SLND) or axillary lymph node dissection (ALND). In part due to early diagnosis and optimised treatment methods, 5-year survival has improved to currently 87%. Despite fewer mastectomies and more BCS, less invasive surgical procedures of the axilla (e.g., fewer ALND vs. SLND), and more refined radiotherapy procedures, late-term upper limb impairments still remain common after primary breast cancer surgery. The most frequent are lymphoedema, sensory disturbances, pain and impaired shoulder function, with up to 70% of patients reporting at least one of these symptoms three years after surgery. These impairments lead to difficulties in activities of daily living, increased risk of depression and anxiety and decreased quality of life (QoL).

Previous international research has primarily focused on prevention and treatment of lymphoedema, and less on other upper limb impairments. Preoperative and early postoperative physiotherapeutic interventions are known to be effective in reducing shoulder pain and improving shoulder function after breast cancer treatment, but there is a lack of international knowledge on the effectiveness of these interventions on the late-term sequelae.

The aim of this trial is to evaluate whether an expert assessment of shoulder impairments, followed by an individualised treatment plan, is superior to a minimal physiotherapeutic rehabilitation program in reducing shoulder symptoms, among women with late-term shoulder impairments after primary breast cancer.

Rational for this study

Currently, no standardised evaluation or treatment of women's late-term shoulder impairments are offered, and it is therefore up to the individual women to seek care, resulting in large variations in rehabilitation. Since half of all cases of breast cancer is diagnosed in women aged 62 years or younger (1), i.e., potentially physically active and in the workforce, an improvement in prevention and management of shoulder impairment after breast surgery may substantially benefit both the patients and society. This randomised trial will potentially have immediate impact on clinical practice as well as on long-term outcomes and quality of life after breast cancer surgery.

Aims and Hypotheses

The primary aim of this trial is to compare the effectiveness of an individualised treatment, relative to a minimal home-based program, on changes in Shoulder Pain and Disability Index (SPADI) from baseline to week 12 after initiating the treatment, in women with late-term shoulder impairments after breast cancer surgery.

The null hypothesis is that there is no difference in SPADI between the two groups. The alternative hypothesis is that women randomised to the individualised treatment (*Intervention group*) will improve more in shoulder function and reduce shoulder pain 12 weeks after initiating the treatment than those randomised to the minimal home-based program (*Control comparator group*).

Objectives

Primary efficacy objective:

To compare the effect of the individualised treatment plan, relative to a minimal physiotherapeutic rehabilitation program, on changes in Shoulder Pain and Disability Index (SPADI) from baseline to 12 weeks after initiating the treatment, in women with late-term shoulder impairments after primary breast cancer surgery.

Key secondary objectives:

To compare the effect of the individualised treatment plan, relative to a minimal physiotherapeutic rehabilitation program, after 12 weeks on changes in the following key secondary outcome measures:

- SPADI pain,
- SPADI function,
- SPADI clinical response,
- Impression of the treatment's success,
- Active Range of Motion (A-ROM),
- Passive Range of Motion (P-ROM),
- Number of treatments received due to shoulder symptoms,
- Maximum shoulder pain intensity,

- Shoulder pain during general activities,
- Shoulder pain at rest,
- Shoulder pain during sleep, and
- Shoulder pain during flexion/rotation/abduction.

Exploratory objectives covered will be published in secondary papers covering the following:

To compare the effect of the individualised treatment plan, relative to a minimal physiotherapeutic rehabilitation program, after 12 weeks on changes in:

- Pain medication consumption,
- Depression score (PHQ-9), and
- Anxiety score (GAD-7).

STUDY METHODS

Trial design

This trial is designed as a stratified (by type of surgery and radiotherapy), block randomised (1:1 allocation), controlled, parallel group and assessor-blinded, single-centre superiority trial conducted in Denmark. Women are recruited from an earlier letter inquiry, based on a register extract, including an invitation to participate in a cross-sectional survey of late-term effects. Women reported shoulder impairments invited to participate in this trial and randomised to an expert assessment of shoulder impairments with an individualised treatment plan or to a 12 week home-based program, which is a minimal intervention within the physiotherapeutic rehabilitation and is delivered in a pamphlet. The two interventions are more described specifically in the trial protocol. The primary endpoint will be assessed at the 12 weeks follow-up, while many of the outcome measures are also collected at 4 and 8 weeks follow-up.

The SAP is reported in accordance with the “*Guidelines for the Content of Statistical Analysis Plans in Clinical Trials*” (2). The trial was registered prior to First Patient First Visit at ClinicalTrials.gov (NCT05277909) and follow the principles of the Declaration of Helsinki (3). The recruitment period started in April 2022 (i.e. First Patient First Visit), and expected to be completed in August 2022 (i.e. Last Patient First Visit).

Randomisation, allocation concealment, and blinding

Eligible participants were randomly assigned in permuted blocks of 2 to 6, with a 1:1 allocation, based on a computer-generated randomisation list generated by an independent data manager implemented into the REDCap randomisation system (4), to either *Intervention group* or *Control group*. Participants were stratified in 5 groups according to type of surgery and +/- radiotherapy treatment:

1. Breast Conserving Surgery (BCS) and Sentinel Lymph Node Dissection (SLND) + radiotherapy;
2. BCS and SLND – radiotherapy;
3. BCS and Axillary Lymph Node Dissection (ALND) + radiotherapy;
4. Mastectomy and SLND – radiotherapy; and
5. Mastectomy and ALND + radiotherapy)

Immediately after obtaining the written informed consent, the baseline measures and outcomes will be collected. The outcome assessors who performed the clinical baseline assessment will also perform the 12-week follow-up, blinded towards treatment allocation. Participants were informed about their group allocation directly after randomisation.

To ensure concealment, the primary investigator, assessors and administrators of the randomisation were blinded to the block sizes, as the randomisation code was stored in REDCap, with no access for the project group.

Sample size and power considerations

The sample size and power estimation were based on the expected between-group difference in the change in SPADI score from baseline to the 12 weeks follow-up. In order to achieve an *a priori* statistical power of at least 85%, with a two-sided significance level $\alpha=0.05$, with an anticipated standard deviation (SD)=15.41 SPADI units (5), the estimated total sample size was n=130 (~ 65 participants in each group), to be able to detect a minimal clinically relevant difference defined as 8 points on the SPADI-score (6,7).

[figure not shown]
Correction:

In the study protocol we estimated an eligible population of approximately n=384 women willing to participate (<https://doi.org/10.1186/s13063-022-06659-1>), based on the cross sectional survey sent to

Individualised treatment vs. a home-based exercise program in women with late-term shoulder impairments after primary breast cancer surgery

approximately 4.300 women in Region of Southern Denmark, corresponding to an expected eligible population rate of 8%.

In fact, we sent out the questionnaire to 9.934 women nationwide, and obtained a participation rate of 56.7% in the cross sectional survey. For the Region of Southern Denmark we received 1.164 complete replies. Of these only 129 women matched the inclusion and exclusion criteria, and furthermore, 76% of these eligible women declined the offer to participate, resulting in $n=31$, corresponding to a much lower than expected, eligible population rate of 2.66%.

Statistical interim analysis and early stopping rules

No statistical interim analyses were planned or done. Patient recruitment stops when a total number of 130 patients have been included and finished their intervention or when the deadline August 31, 2022 is reached.

Timing of final analysis

The final analysis for the between group comparison (*Intervention group vs. Control comparator group*) for the primary endpoint (baseline, 4-, 8- and 12-weeks follow-up) is planned to be performed after the last randomised patient has completed the 12 weeks follow-up. The publication of the trial will be prepared when the data have been received and cleaned (anticipated by April 2023).

Timing of outcome assessments

The overview of the trial time-points of each outcome assessment is presented in the **Table 1** in the study protocol at the TRIALS journal (<https://doi.org/10.1186/s13063-022-06659-1>): “*Effectiveness of an expert assessment and individualised treatment compared with a minimal home-based exercise program in women with late-term shoulder impairments after primary breast cancer: Study protocol for a randomised controlled trial*”. The intervention start date (*Intervention group* or *Control comparator group*) for each patient is used to calculate the 4-, 8-, and 12-weeks follow-up time points.

STATISTICAL PRINCIPLES

Confidence intervals and p-values

All 95% confidence intervals (95% CIs), and *P-values* will be two sided. Adjustments for multiplicity will not be applied, but rather the analyses of the key secondary outcomes will be performed and interpreted in a prioritized order. The analyses of the confirmatory secondary outcomes will be performed in sequence until one of the analyses fails to show the statistically significant difference, or until all analyses have been completed at a statistical significance level of 0.05. The key secondary statistical tests will be reported with *P* values for hypothesis tests and claims of statistical significance.

Analysis populations

The primary analyses will be based on the Intention to Treat (ITT) population, i.e., based on the Full Analysis Set (having the outcome of interest measured at baseline). The ITT principle asserts the effect of a treatment policy (that is, the planned treatment regimen), rather than the actual

treatment given (i.e., it is independent of treatment adherence). Accordingly, participants allocated to a treatment group will be followed up, assessed and analysed as members of that group, irrespective of their adherence to the planned course of treatment (i.e., independent of withdrawals and cross-over phenomena) (8).

TRIAL POPULATION

Screening data

The total number of patients, screened for eligibility, will be collected, and presented in a CONSORT Flow Diagram ([Figure 1](#)) for documenting the flow of participants through the trial. The number of ineligible patients randomised by mistake, if any, will be reported including reason for ineligibility.

Eligibility criteria

Women who have participated in a parallel performed nationwide cross-sectional survey study and reported shoulder pain or impairment as their primary discomfort after BCS or mastectomy combined with either SLND or ALND due to breast cancer, and fulfilling the following inclusion and exclusion criteria are considered eligible for the randomised trial:

Inclusion criteria

1. Breast cancer patients who underwent unilateral BCS or mastectomy on the left or right side, including SLND or +/- ALND within the last 3-7 years (2015-2019)
2. Currently living in the Region of Southern Denmark or Central Denmark Region with a radius of 75 km from Vejle Hospital
3. Between 18 and 71 age at the time of surgery for primary breast cancer
4. Indicate pain in chest and/or shoulder area (shoulder impairments) as the biggest problem/late-term effect in everyday life
5. Indicate impaired shoulder function due to pain or due to tightness/tension
6. Indicate shoulder pain at rest, during general activities, during sleep or during flexion, rotation or abduction of the shoulder
7. A score ≥ 15 on the Disabilities of the Arm, Shoulder and Hand (Quick DASH) (9,10)
8. Agree to participate in this trial and sign written informed consent.

Exclusion criteria

1. No previous breast cancer (before 2014)
2. Cancer relapse after the date of index surgery, cancer spread outside of thorax and axilla, tumour fixed to chest wall
3. Primary- or secondary breast reconstruction performed at any time
4. Severe lymphedema (an average score $\geq 70\%$ in the first 7 questionnaires on the LYMPH-ICF-DK (11,12))
5. Bilateral breast cancer surgery
6. Previous surgery in the affected shoulder (prior to inclusion)
7. Previous shoulder or upper limb fractures (left/right)
8. Currently receiving chemo, immuno- or radiotherapy
9. Co-morbidity expected to influence shoulder function (e.g. rheumatoid arthritis, previous stroke, multiple sclerosis)
10. Other reasons for exclusion (e.g. pregnancy, not legally competent, unable to comprehend the information or unable to consent)

Recruitment

The CONSORT Flow Diagram will comprise number of patients screened, excluded (with reasons), randomised, stratified, receiving their allocated treatment, withdrawals (with reasons), and lost to follow-up (with reasons) and included in ITT analysis. The anticipated CONSORT Flow Diagram is depicted in [Figure 1](#).

Withdrawal/follow-up

The reason for each crossover or withdrawal will be registered. Participants performing a crossover will remain in the study and be analysed following the intention-to-treat principle (i.e., remaining in their original group). The level of consent withdrawal will be classified as:

1. consent to continue follow-up and data collection;
2. consent to continue data collection only; or
3. complete withdrawal with no further follow-up and data collection (13).

In the CONSORT Flow Diagram numbers and reasons for withdrawal and/or loss to follow-up will be presented given at the 4-, 8- and 12-weeks (primary end point) outcome assessment; separately for the two intervention groups.

Baseline characteristics

The following data will be used to describe patients by randomisation group at baseline: mean age, height, weight, body mass index (BMI), smoking, alcohol consumption, highest education level, employment, index shoulder, dominant side affected, duration of shoulder symptoms, pain medication consumption due to shoulder related pain, depression, anxiety and outcome measures will be collected at baseline. The baseline characteristics are illustrated in [Table 1](#).

Categorical variables will be calculated and presented in numbers and percentages. While Means and Standard Deviations (SDs) will be calculated and presented for continuous variables if data follows a normal distribution; in case, continuous variables does not appear to follow normal distribution, median and interquartile range will be calculated. No tests of statistical significance will be conducted for baseline characteristics.

ANALYSIS

Primary outcome

Shoulder Pain and Disability Index (SPADI) [Time Frame: 0, 4, 8 and 12 weeks]

The primary outcome measure will be the between-group difference in change in SPADI-score ($\Delta\text{SPADI}_{12} = \text{SPADI}_{12\text{-weeks follow-up}} - \text{SPADI}_{\text{baseline}}$) from baseline to 12 weeks after initiating the treatment. SPADI is considered a valid, reliable, and responsive patient-reported questionnaire assessing shoulder pain and function, where each domain score is equally weighted and added to a total percentage score that ranges from 0 (best) to 100 (worst) (9,14) ([Figure 2](#)).

Key secondary outcomes

- *SPADI pain [Time Frame: 0, 4, 8 and 12 weeks]*

A key secondary outcome will be the between-group difference in change in a separate SPADI-pain-subscale ($\Delta\text{SPADIpain}_{12} = \text{SPADIpain}_{12\text{-weeks follow-up}} - \text{SPADIpain}_{\text{baseline}}$) from baseline to 12 weeks after initiating the treatment. SPADI is considered a valid and reliable

patient-reported questionnaire consisting of 5-item pain subscale are scored on a numeric rating scale that ranges from 0 (no pain) to 10 (worst pain) (9,14).

- *SPADI function [Time Frame: 0, 4, 8 and 12 weeks]*

A key secondary outcome will be the between-group difference in change in a separate SPADI-function-subscale ($\Delta\text{SPADI}_{\text{funcion}}_{12} = \text{SPADI}_{\text{funcion}}_{12\text{-weeks follow-up}} - \text{SPADI}_{\text{funcion}}_{\text{baseline}}$) from baseline to 12 weeks after initiating the treatment. SPADI is a valid and reliable patient-reported questionnaire consisting of 6-item pain subscale (exclusion of question three and seven) are scored on a numeric rating scale that ranges from 0 (no difficulty) to 10 (so difficult that required help) (9,14).

- *SPADI clinical response [Time Frame: 12 weeks (follow-up)]*

Response to treatment will be computed for the SPADI change score for each woman in both treatment groups and presented dichotomised (i.e. responder and non-responder) as number (and percentages) responders. Women will be classified as a responder if the SPADI change score improves by 8 points or more (\geq), corresponding to the minimal clinically important difference on SPADI (6,7) from baseline to 12 weeks follow-up.

- *Global perceived effect (GPE) [Time Frame: 4, 8 and 12 weeks]*

A key secondary outcome will be the between-group difference in GPE score 12 weeks after initiating the treatment.

The GPE will evaluate the impression of the treatment's success including overall shoulder problems on a 7-point Likert scale ranging from “markedly worse” to “markedly improved” (15,16).

- *Active Range of Motion (A-ROM) [Time Frame: 0 and 12 weeks]*

A key secondary outcome will be the between-group difference in change in A-ROM degrees ($\Delta\text{A-ROM}_{12} = \text{A-ROM}_{12\text{-weeks follow-up}} - \text{A-ROM}_{\text{baseline}}$) from baseline to 12 weeks after initiating the treatment. The smartphone inclinometer (GetMyROM) is considered valid and reliable to assess A-ROM in flexion, internal rotation, external rotation and abduction (17-21).

- *Passive Range of Motion (P-ROM) [Time Frame: 0 and 12 weeks]*

A key secondary outcome will be the between-group difference in change in P-ROM degrees ($\Delta P-ROM_{12} = P-ROM_{12\text{-weeks follow-up}} - P-ROM_{\text{baseline}}$) from baseline to 12 weeks after initiating the treatment. The smartphone inclinometer (GetMyROM) is considered valid and reliable to assess A-ROM in flexion, internal rotation, external rotation and abduction (17-21).

- *Number of treatments received due to shoulder symptoms [Time Frame: 12 weeks (follow-up)]*

A key secondary outcome will be the between-group difference in mean number of treatments received due to shoulder symptoms from baseline to 12 weeks after initiating the treatment.

- *Maximum shoulder pain intensity [Time Frame: 0, 4, 8 and 12 weeks]*

A key secondary outcome will be the between-group difference in change in maximum pain intensity ($\Delta MaxPain_{12} = MaxPain_{12\text{-weeks follow-up}} - MaxPain_{\text{baseline}}$) from baseline to 12 weeks after initiating the treatment. The Numeric Rating Scale (NRS) is considered a valid, reliable and responsible single 11-item patient-reported pain scale that ranges from 0 (no pain) to 10 (worst pain) (22).

- *Shoulder pain during general activities [Time Frame: 0, 4, 8 and 12 weeks]*

A key secondary outcome will be the between-group difference in change in shoulder pain during general activities ($\Delta General\ activity\ pain_{12} = General\ activity\ pain_{12\text{-weeks follow-up}} - General\ activity\ pain_{\text{baseline}}$) from baseline to 12 weeks after initiating the treatment. The NRS is considered a valid, reliable and responsible single 11-item patient-reported pain scale that ranges from 0 (no pain) to 10 (worst pain) (22).

- *Shoulder pain at rest [Time Frame: 0, 4, 8 and 12 weeks]*

A key secondary outcome will be the between-group difference in change in shoulder pain at rest ($\Delta Pain\ at\ rest_{12} = Pain\ at\ rest_{12\text{-weeks follow-up}} - Pain\ at\ rest_{\text{baseline}}$) from baseline to 12 weeks after initiating the treatment. The NRS is considered a valid, reliable and responsible single

11-item patient-reported pain scale that ranges from 0 (no pain) to 10 (worst pain) (22).

- *Shoulder pain during sleep [Time Frame: 0, 4, 8 and 12 weeks]*

A key secondary outcome will be the between-group difference in change in shoulder pain during sleep (Δ Pain during sleep₁₂ = Pain during sleep_{12-weeks follow-up} – Pain during sleep_{baseline}) from baseline to 12 weeks after initiating the treatment. The NRS is a valid, reliable and responsible single 11-item patient-reported pain scale that ranges from 0 (no pain) to 10 (worst pain) (22).

- *Shoulder pain during flexion/rotation/abduction [Time Frame: 0 and 12 weeks]*

A key secondary outcome will be the between-group difference in change in shoulder pain during flexion/rotation/abduction (Δ Pain during flex rot abd₁₂ = Pain during flex rot abd_{12-weeks follow-up} – Pain during flex rot abd_{baseline}) from baseline to 12 weeks after initiating the treatment. The NRS is a valid, reliable and responsible single 11-item patient-reported pain scale that ranges from 0 (no pain) to 10 (worst pain) (22).

The primary and key secondary outcomes will be presented as illustrated in **Table 2**.

Analysis methods

The CONSORT guideline (13) will be followed for all trial reporting aspects, as recommended by the “*Enhancing the QUAlity and Transparency Of health Research*” (EQUATOR) network website (23).

The primary (continuous) outcome will be analysed by using repeated measures mixed effects models, including participants as a random effect, with fixed effect factors for group (2 levels) and week (4 levels for the SPADI questionnaire [weeks 0, 4, 8, and 12]), the stratification factors and the interaction between group and week, adjusted for baseline values. To assess the adequacy of the linear models describing the observed data—and checking assumptions for the systematic and the random parts of the models—the model features will be investigated via the predicted values and the studentized residuals; that is, the residuals have to be normally distributed (around 0) and be independent of the predicted values. Results will be expressed based on least squares mean estimates with standard errors (SE) as well as the differences in the least squares means with 95% CIs to represent precision of the contrast between groups. Further, for the primary

outcome, a 95% CI excluding differences greater than 4 SPADI points between groups will be interpreted as indicating absence of a clinically meaningful difference. Dichotomous outcome variables will be analysed with logistic regression, with identical fixed effect factors and covariates as the mixed linear model described above. Missing data for dichotomous outcomes will be computed based on conservative (non-responder) imputations.

Subgroup analyses (24) will be used to examine whether the observed overall treatment effect varies across participants subgroups, and to whether the effect is modified by the value of a variable assessed at baseline, analysed by the following thresholds: median age, median duration of shoulder symptoms, obesity ($BMI \geq 30 \text{ kg/m}^2$), dominant side affected (left vs right). This statistical approach to evaluate potential effect modifiers, will be a test for statistical interaction whether the treatment effect (net benefit on change in the SPADI score) varies across levels of the effect modifier (25).

Missing data and sensitivity analyses

To handle missing data, repeated-measures linear mixed effects models will be used (26-29). These models are considered valid if data are “*Missing at Random*” (i.e., any systematic difference between the missing values and the observed values can be explained by differences in observed data) (30).

The following four strategies for handling and interpretation of missing data will be applied in the sensitivity analysis:

1. We will attempt to follow up all randomised participants, even if they withdraw from allocated treatment (i.e., contact all individuals unless they explicitly stated that they had withdrawn their consent);
2. Perform a main analysis of all observed data that are valid under a plausible assumption about the missing data (i.e., data as randomised; using linear mixed effects models, assuming that data are “*Missing at Random*”);
3. Perform sensitivity analyses to explore the effect of departures from the assumption made in the main analysis (i.e., non-responder-imputation: using the value at baseline to replace missing data);

these models will be informative about the robustness in case data are “*Missing Not At Random*”); and

4. Account for all randomised participants, at least in the sensitivity analyses (including strategy 2 and 3, plus the corresponding analyses based on the per protocol population) (28).

Thus, the following sensitivity analyses will be performed on various population analyses, including a non-responder imputation and per-protocol, to examine the robustness by revealed similar results in these sensitivity analyses. Robustness is a concept that refers to the sensitivity of the overall conclusions to various limitations of the data, assumptions, and analytic approaches to data analysis. Robustness implies that the treatment effect and primary conclusions of the trial are not substantially affected when analyses are carried out based on alternative assumptions or analytic approaches.

Additional analyse

No additional analyses on the primary and key secondary outcomes are planned from baseline to 12 weeks follow-up.

Harms

Serious adverse events (SAE) will be categorised in accordance with the definitions established by the United States Food and Drug Administration (e.g. hospitalisation or death) (31). All categorical types of SAE's will be presented for each group and statistical tested by using logistic regression. The SAEs will be presented as illustrated in **Table 3**.

Statistical software

All data analysis will follow the statistical methods described above, and will be performed applying STATA (Statacorp, College Station, Texas, USA) and SAS (SAS Institute Inc., Cary, North Carolina, USA) software.

REFERENCES

1. American Cancer Society. Breast Cancer Facts & Figures 2019-2020 [Internet]. 2020 [cited 2022 Aug 08, pp. 4]. Available from: <https://www.cancer.org/content/dam/cancer-org/research/cancer-facts-and-statistics/breast-cancer-facts-and-figures/breast-cancer-facts-and-figures-2019-2020.pdf>
3. World Medical Association (WMA). WMA Declaration of Helsinki – Ethical Principles for Medical Research Involving Human Subjects [Internet]. 1964 [cited 2018 Aug 14]. Available from: <https://www.wma.net/policies-post/wma-declaration-of-helsinki-ethical-principles-for-medical-research-involving-human-subjects>

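### The ordered testing of key secondary outcomes is not made conditional on a significant primary, so a confirmatory SPADI pain claim can follow a failed SPADI total

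*SAP*

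**What the plan says.** The Methods paragraph of the SAP's opening summary describes the trial as a "two-group comparison testing superiority hypothesis related to the primary and key secondary objectives". The section on sample size plans the primary comparison for "statistical power of at least 85%, with a two-sided significance level" of 0.05.

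The section on confidence intervals and p-values sets the multiplicity rule: "Adjustments for multiplicity will not be applied, but rather the analyses of the key secondary outcomes will be performed and interpreted in a prioritized order". Next comes the stopping rule: "The analyses of the confirmatory secondary outcomes will be performed in sequence until one of the analyses fails to show the statistically significant difference". Otherwise testing runs to the end of the list. The summary repeats the rule and adds that the tests are two-sided: "until all analyses have been completed at a two-sided statistical significance level of 0.05". The key secondary tests are to be reported with P "values for hypothesis tests and claims of statistical significance".

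The key secondary objectives compare the groups "after 12 weeks on changes in the following key secondary outcome measures", and the list that follows begins with SPADI pain. The outcome descriptions and Table 2 begin with it too. Under the primary outcome, SPADI total is defined so that "each domain score is equally weighted and added to a total percentage score".

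**The concern.** A fixed sequence protects the error rate only over the tests inside it. Here the primary stands outside. It has its own 0.05, and the secondary sequence has another 0.05 whether or not the primary succeeds. The SAP calls the secondary outcomes confirmatory and attaches significance claims to them, so they are not merely descriptive.

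What is at stake is the reading of a negative trial. If SPADI total is not significant, the rule still lets the report declare a confirmed effect on SPADI pain, which is one of the two equally weighted parts of that same total. The report could then state no demonstrated effect on the primary beside a confirmed effect on half of it, fully in line with the plan.

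**Working it through.** **Alpha spent on the primary.** Inputs from the sample size section: difference 8, SD 15.41, two-sided 0.05, power 85%. The normal formula gives 2 × [15.41 × (1.960 + 1.036) / 8]² = 66.6, so 67 per arm (134 in total) against the stated 65 (130). Power at 65 per arm is 84.1% (83.6% with the t-test). A one-sided 0.05 would need only 54 per arm. The stated size therefore fits a primary that uses the whole two-sided 0.05, leaving none for the secondaries.

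**The secondary sequence alone.** The first true null that is reached is tested at 0.05, and failure there ends the sequence. Its own error is at most 5%.

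**Primary and sequence together, both nulls true.** Take SPADI pain as the first step. Later steps are reached only if SPADI pain has already been claimed, so they cannot add to the chance of at least one false claim when SPADI pain is null. The quantity needed is P(|Z1| > 1.96 or |Z2| > 1.96), with Z1 the test of SPADI total and Z2 the test of SPADI pain.

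Since the total is pain plus function with equal weight, let r be the pain-function correlation and k = SD(function) / SD(pain). Then

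c = corr(Z1, Z2) = (1 + rk) / √(1 + k² + 2rk), which is √((1 + r)/2) when k = 1.

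The SAP gives neither r nor k, so both are assumptions. Bivariate normal results for k = 1:

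| r | c | At least one false claim | Excess over 5.0% |
|---|---|---|---|
| 0.3 | 0.806 | 7.8% | 2.8 points |
| 0.5 | 0.866 | 7.3% | 2.3 points |
| 0.7 | 0.922 | 6.8% | 1.8 points |
| 0.9 | 0.975 | 6.0% | 1.0 point |

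With unequal domain SDs, at r = 0.3, 0.5, 0.7, 0.9:

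- k = 0.5: 6.79%, 6.53%, 6.19%, 5.69%
- k = 2: 8.59%, 8.06%, 7.39%, 6.39%

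The range over these settings is 5.7% to 8.6%.

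**Simulation check.** Two-sample t-tests, 65 per arm, 100,000 draws, k = 1, gave 7.79%, 7.39%, 6.85% and 5.88% for the same four r, with a simulation error of about 0.08 points. The last is about two simulation errors below the formula. The primary alone rejected in 4.97%, 4.98%, 5.02% and 4.91%.

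**With a gate.** A false claim on either outcome then requires a significant primary first, so under the same nulls the probability is 5.0%.

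**Other configurations.**

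- Primary effect real: rejecting the primary is no error, and the sequence holds 5%. No excess.
- Primary null true, SPADI pain effect real: a SPADI pain claim is not a false positive. An excess arises only if the sequence goes on to a later outcome whose null is true.

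**The case against.** The strongest reply is that a gate is implied. The SAP always places the primary ahead of the secondaries, speaks of a prioritised order, and nowhere says that the secondaries will be tested whatever the primary shows. That is fair as to intention: a reader might infer that the trial means to ignore a failed primary, and the documents do not support that. But the rule as written names only secondary outcomes as steps and gives only their failure as a reason to stop. Someone following it literally would not stop at a failed primary.

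The excess is also modest, rests on assumed correlations and arises only under particular nulls. The primary test keeps its own 5%, and Table 2 shows the primary above its components. All of that stands and limits the weight of the point.

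Three stronger readings should be set aside:

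- **That the joint error exceeds 5% whenever the primary null is true.** A true null among the secondaries actually reached is needed as well.
- **That the joint error is 1 − 0.95² = 9.75%.** That needs a first secondary uncorrelated with the primary. The objectives, outcome descriptions and Table 2 all put SPADI pain first, and it is part of the primary score. Their agreement also makes list order the natural testing order, though no sentence says so.
- **That the 4-point rule under the analysis methods shows secondary testing was meant to continue after a negative primary.** It only says how to interpret a confidence interval and is not a testing rule.

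**Conclusion.** The point holds as a gap in the testing rule. The ordered testing covers only the key secondary outcomes, and its start does not depend on a significant SPADI total, so the plan as written permits a confirmatory SPADI pain claim after a failed primary.

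With both nulls true and SPADI pain tested first, the chance of a false claim on the two is about 6.0% to 7.8% with equal domain SDs, and 5.7% to 8.6% over SD ratios of 0.5 to 2, where 5% would be expected. These figures rest on assumed pain-function correlations of 0.3 to 0.9 and on approximately normal test statistics. The validity of the primary analysis is not in question. The plan should be amended because the remedy is simple and the claim at risk concerns a component of the primary itself.

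**What to change.** In the section on confidence intervals and p-values, and in the matching sentence of the summary, state that:

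- SPADI total at 12 weeks is step 1, tested at two-sided 0.05.
- The key secondary outcomes are tested for confirmatory claims only if step 1 is significant, each at two-sided 0.05, in the order listed under the key secondary objectives, stopping at the first non-significant result.
- If step 1 is not significant, they are reported with estimates and 95% confidence intervals and without confirmatory claims.

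This takes one or two sentences before unblinding, with no new data and no change in sample size. The real cost is that no secondary outcome can support a confirmatory claim if the primary fails.
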